9.2 Subject Accountability

A summary of study reporting period and analysis set dispositions will also be prepared.

Key study dates for the first subject enrolled, last subject enrolled and last subject's end of study included any other key study dates that are relevant for the study design (e.g., last subject's end of IP, data cutoff date) will be presented.

The number and percent of subjects who were randomized, received IP, completed IP, discontinued IP and reason for discontinuing, completed study, discontinued study and reason for discontinuing will be summarized by dose phase (SAD cohorts in Part A and MAD cohorts in Parts B to C) and actual treatment group.

The number and percent of subjects randomized will be tabulated by study site. Listings may be generated and reviewed but may not be included in the clinical study report (CSR).

9.3 Important Protocol Deviations

IPDs categories are defined by the study team before the first subject's initial visit and updated during the IPD reviews throughout the study prior to database lock. These definitions of IPD categories, subcategory codes, and descriptions will be used during the course of the study. Eligibility deviations are defined in the protocol.

9.4 Demographic and Baseline Characteristics

Demographic (i.e., age, age groups [<40 , ≥ 40], sex, race, ethnicity) and baseline characteristics (height, weight, waist circumference, BMI, medical history) will be summarized by dose phase (SAD cohorts in Part A and MAD cohorts in Parts B to C), actual treatment group and overall (i.e., total from all the cohorts involved in the analysis and irrespective of the randomized treatment) using descriptive statistics. If multiple

races have been reported for a subject, the subject will be categorized as multiple race as well as by the combination of race.

9.5 Efficacy Analyses

Not applicable.

9.6 Safety Analyses

9.6.1 Analyses of Primary Safety Endpoint(s)

A table summarizing the primary endpoints and planned analysis methods is shown below:

Table 9-1. Primary Endpoint Summary Table

| Endpoint | Statistical Analysis Method | Sensitivity Analysis |
|--|---|-----------------------------|
| Subject incidence of TEAEs | 
The following analyses will be performed on the FAS and summarized by dose phase (SAD cohorts in Part A and MAD cohorts in Parts B to C) and actual treatment group.
 
Subject incidence tabulated by system organ class (SOC), high level term (HLT), and preferred term (PT) of
 
 • TEAEs • fatal AEs • serious adverse events (SAEs) • AEs leading to withdrawal from IP or other protocol-required therapies | None |
| Changes in laboratory safety tests, vital signs and 12-lead ECGs | 
The following analyses will be performed on the FAS and summarized by dose phase (SAD cohorts in Part A and MAD cohorts in Parts B to C) and actual treatment group at protocol-specified scheduled visit.
 
Summary statistics of
 
 • change from baseline safety laboratory test results | None |

| | | |
|--|--|--|
| | 
• change from baseline vital signs• change from baseline ECG parameters | |
|--|--|--|

9.6.2 Adverse Events

The Medical Dictionary for Regulatory Activities (MedDRA) version 23.0 or later will be used to code all events categorized as AEs to SOC, HLT, and PT. All AE tables will be summarized by dose phase (SAD cohorts in Part A and MAD cohorts in Parts B to C) and actual treatment group.

The subject incidence of AEs will be summarized for all TEAEs, SAEs, TEAEs leading to withdrawal of IP, fatal AEs, and events of interest (EOIs).

Subject incidence of all TEAEs, SAEs, TEAE's leading to withdrawal of IP, and fatal AEs will be tabulated by SOC, HLT, and PT in descending order frequency.

Subject incidence of EOIs will also be summarized according EOI search categories and PT if applicable. Nausea and vomiting are identified using a broad search scope in a standardized MedDRA query (SMQ) of gastrointestinal nonspecific inflammation and dysfunctional conditions. Hypersensitivity is identified using a narrow search scope in SMQ. Immunogenicity and injection site reactions are identified using a broad search scope in Amgen-defined MedDRA search strategies.

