4.3 Justification for Investigational Product Dose

The planned cohort in this amendment of the study consists of a multiple-dose cohort following a titration schema as presented in [Figure 1-1](#).

Previously, subjects in Part A received single doses of AMG 133 - 21, 70, 140, 280, 560, and 840 mg administered SC. This part also consisted of an IV cohort (cohort 6) at a dose of 70 mg administered IV; **all SAD** have been completed. The starting dose and exposure multiples for the doses evaluated in SAD were calculated based on the NOAELs determined in the 13-week Good Laboratory Practices repeat-dose mouse and cynomolgus monkey nonhuman primate toxicology studies (every 2 weeks dosing, Section 2.2.2.3) and the observed reduction in body weight in the chronic efficacy study in obese cynomolgus monkeys.

Part B consisted of evaluation of AMG 133 **following repeat doses - 140, 280, and 420 mg administered Q4W for a total of 3 doses per cohort.** Preliminary review of the PK data in the FIH SAD **and MAD** part of the study demonstrated that AMG 133 pharmacokinetics follow a linear, dose proportional kinetics based on C_{max} (area under the curve [AUC] data pending), with a half-life of approximately **15 to 20 days**.

For **SAD cohorts 1 to 6 and 11**, no **serious adverse events** or deaths have been reported, and most **adverse events** reported were mild associated with nausea, vomiting, **and dyspepsia**. One subject in cohort 3 (140 mg dose) had a moderate adverse event associated with gastroenteritis **related to IP**. **Approximately 90% of subjects enrolled in MAD cohorts 7 to 10 reported mild GI-related adverse events (mainly nausea, vomiting, and diarrhea) after the first dose of AMG 133 and less than 5% experienced GI-related adverse events after the second dose.** There were **no serious adverse events or deaths reported after any of the doses**.

Approximately 26% of subjects in the MAD trial discontinued the study prior to

receiving the second dose which caused concerns regarding tolerability of the first dose; 50% of subjects in cohort 9 withdrew consent after receiving the 420 mg dose on day 1 due to GI-related adverse events. The doses were selected to allow for whole integer injection volumes to circumvent any potential dosing errors.

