Part C consists of two cohorts (cohorts 12 and 13), both open-label to evaluate dose-level escalation from 70 mg to 420 mg. The objective of Part C is to evaluate first dose effects of AMG 133 on GI-related adverse events using a titration methodology. Cohort 12 will start at a lower dose [redacted] mg) of AMG 133 given [redacted]

Cohort 13 will start at a lower dose ([redacted] mg) of AMG 133 given [redacted]

The rationale for dose selection for Part C is based on the available PK data from this ongoing FIH study cohorts 1 to 11 (Part A and Part B) and the NOAEL exposures established based on 13-week GLP repeat-dose studies in mouse and cynomolgus monkeys.

Similarly, for cohort 12, the predicted human exposure multiples for intact AMG 133 following the second dose of [redacted] mg on Day [redacted] are approximately 40.5-fold and 45-fold for C_{max} and AUC_{ss} , respectively, based on NOAEL established in cynomolgus monkeys, and 43-fold and 42.4-fold for C_{max} and AUC_{ss} , respectively, based on NOAEL established in mice. The predicted human exposure multiples for total AMG 133 following the second dose of [redacted] mg on Day [redacted] are approximately 45-fold and 49-fold for C_{max} and AUC_{ss} , respectively, based on NOAEL established in cynomolgus monkeys, and 54-fold and 42-fold for C_{max} and AUC_{ss} , respectively, based on NOAEL established in mice (Table 8 and Table 9).

For cohort 13, the predicted human exposure multiples for intact AMG 133 following the second dose of [redacted] mg on Day [redacted] are approximately 39-fold and 43.2-fold for C_{max} and AUC_{ss} , respectively, based on NOAEL established in cynomolgus monkeys, and 41.3-fold and 40.6-fold for C_{max} and AUC_{ss} , respectively, based on NOAEL established in mice. The predicted human exposure multiples for total AMG 133 following the second dose of [redacted] mg on

Day █ are approximately 42.2-fold and 45.5-fold for C_{max} and AUC_{ss} , respectively, based on NOAEL established in cynomolgus monkeys, and 50.9-fold and 47.5-fold for C_{max} and AUC_{ss} , respectively, based on NOAEL established in mice (Table 8 and Table 9).

Table 8. Estimated Exposure Margins of Intact AMG 133 Following Repeat Doses (Q4W)

Clinical Dose (mg)	Route	Predicted Human Exposure		Predicted Exposure Multiples ^a			
		AUC ₀₋₂₈ (μ g·hr/mL)	C_{max} (μ g/mL)	Mouse ^b		Monkey ^c	
█ (cohort 12) ^f	SC	17 731	37	42.4	43	45.1	40.5
█ (cohort 13) ^f	SC	18 513.6	38.5	40.6	41.3	43.2	39

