9.4.2 Methods of Analyses

9.4.2.1 General Considerations

Descriptive statistics will be provided for selected demographics, safety, pharmacokinetic, and pharmacodynamic endpoints. Accumulating pharmacodynamic data might be reviewed throughout the study by treatment, periodically. Descriptive statistics on continuous measurements will include means, medians, 25th and 75th percentiles, standard deviations and ranges, while categorical data will be summarized using frequency counts and percentages. Pharmacokinetic, pharmacodynamic, and clinical laboratory data will be summarized by treatment group and at each time point when samples are collected. Graphical summaries of the data may also be presented.

Data for subjects receiving placebo will be combined across cohorts 1 to 5 and cohort 11 (SC) and cohort 6 (IV), except for adverse events where the combined SC cohorts will be summarized separately from the IV cohort within Part A.

Data for subjects receiving the placebo will be combined across cohorts 7 to 9 within Part B and data for subjects receiving placebo from cohort 10 will be summarized separately. **Part C is an open-label study, therefore, data for subjects from cohorts 12 to 13 will be summarized separately.**

Data for subjects receiving AMG 133 will be presented separately by cohort. When data are summarized by time, the values recorded against the scheduled time points listed in the protocol will be used. When assessing minimum/maximum increases or decreases over the study, all assessments, including unscheduled assessments will be used.

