9.4.2.3.2 Adverse Events

Subject incidence of all treatment-emergent adverse events will be tabulated by system organ class and preferred term. Tables of fatal adverse events, serious adverse events, adverse events leading to withdrawal from investigational product or other protocol-required therapies, and treatment-emergent adverse events will also be provided. The number and percentage of subjects reporting adverse events will be evaluated for each dose cohort, across dose cohorts, and will also be tabulated by relationship to study drug. Adverse events resulting in treatment discontinuation will be identified.

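### Part C is meant to evaluate first-dose GI events under titration, but no readable adverse event table separates the starting dose from the escalation

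*SAP*

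**What the plan says.** **Purpose of Part C.** Protocol 4.3 states: "The objective of Part C is to evaluate first dose effects of AMG 133 on GI-related adverse events using a titration methodology". The two cohorts are open-label, "to evaluate dose-level escalation from 70 mg to 420 mg". The background in the same section is by dose: about 90% of subjects in cohorts 7 to 10 had mild GI events after the first dose and "less than 5% experienced GI-related adverse events after the second dose". It also reports that "50% of subjects in cohort 9 withdrew consent after receiving the 420 mg dose on day 1 due to GI-related adverse events".

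**Planned adverse event tables.** SAP 9.6.2 says that all adverse event "tables will be summarized by dose phase (SAD cohorts in Part A and MAD cohorts in Parts B to C) and actual treatment group". Dose phase there means single-dose versus multiple-dose cohorts, not the step within a subject. For events of interest, which include nausea and vomiting: "Subject incidence of EOIs will also be summarized according EOI search categories and PT if applicable". SAP Table 9-1 lists no sensitivity analysis for treatment-emergent events. SAP section 5 counts an event as treatment-emergent from the first dose to the end of study, with no reset at later doses.

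**What the protocol adds.** Section 9.4.2.3.2: "The number and percentage of subjects reporting adverse events will be evaluated for each dose cohort, across dose cohorts". Section 9.4.2.1, for Part C: "data for subjects from cohorts 12 to 13 will be summarized separately". SAP section 10 withdraws only the tabulation by relationship to study drug, so the view by cohort stands.

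**The concern.** In cohorts 12 and 13 the dose rises within each subject. A cumulative yes/no per subject merges events at the low starting dose with events after the step up. Those two patterns mean different things for a titration scheme. In one, the starting dose itself provokes the events; in the other, titration only delays them until the higher dose is reached.

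The sponsor's own argument for Part C rests on a contrast between first and second doses in Part B. The planned tables could not reproduce that contrast for Part B or show its counterpart for Part C. What is at stake is how Part C can be read on the question that section 4.3 sets for it.

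**Working it through.** **1. The plan's own figure.** The only statistical figures given are the chances of seeing at least one event among 87 subjects on AMG 133 (Protocol 9.2, SAP 3.2). The formula 1 − (1 − p)^87 gives 92.9% at p = 3% and 98.8% at p = 5%. Both reproduce. They concern the whole study and are not in dispute.

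**2. Dosing days (Protocol 1.3, Tables 3 to 6).**
- Cohorts 7 to 10: days 1, 29, 57; gaps of 28 and 28 days.
- Cohort 12: days 1, 8, 15, 43; gaps of 7, 7 and 28 days.
- Cohort 13: days 1, 8, 15, 22, 29, 57; gaps of 7, 7, 7, 7 and 28 days.

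The doses on each Part C day are redacted. The synopsis requires overnight observation after the first dose of a further level, on day 15 (cohort 12) or day 29 (cohort 13). By inference there are 2 starting and 2 escalated doses in cohort 12, and 4 and 2 in cohort 13.

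**3. What a cumulative count hides in Part B.** With 90% after dose 1 and at most 5% after dose 2, incidence through dose 2 lies between max(90, 5) = 90% and 90 + 5 = 95%. The drop of at least 85 points between doses does not appear. Section 4.3 gives no denominators for these percentages, and about 26% of subjects left before dose 2.

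**4. What it hides in Part C (assumed rates, independence between steps).** Cumulative incidence = 1 − (1 − p_start)(1 − p_step).
- 90% then 5%: 1 − 0.10 × 0.95 = 90.5%.
- 5% then 90%: 1 − 0.95 × 0.10 = 90.5%.
- 20% then 60%, and 60% then 20%: 1 − 0.80 × 0.40 = 68% both ways.

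Opposite patterns give the same table entry.

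**5. By counting alone.** If x of n subjects have any event, the number with one after the step up can be anything from 0 to x. Exact (Clopper-Pearson) 95% intervals for illustrative counts:

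| Overall | Lowest possible after step | Highest possible after step |
|---|---|---|
| 5/6 | 0/6 (0 to 45.9%) | 5/6 (35.9 to 99.6%) |
| 11/12 | 0/12 (0 to 26.5%) | 11/12 (61.5 to 99.8%) |

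**6. Why the window must be fixed.** Assigning each event to the last dose before onset would give a starting dose in Part C 7 days at risk and the first dose in cohort 9 28 days. At a constant background rate the latter expects 28/7 = 4 times as many onsets, which would favour titration. A common window of 7 days, the shortest scheduled gap, removes this.

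**7. Why one dose cannot be isolated.** Section 4.3 gives a half-life of 15 to 20 days. Assuming simple exponential elimination, the fraction left after 7 days is 0.5^(7/15) = 0.72 to 0.5^(7/20) = 0.78. After 28 days it is 0.5^(28/15) = 0.27 to 0.5^(28/20) = 0.38. Weekly starting doses therefore accumulate.

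**The case against.** The strongest case against the point is that the SAP delivers the formal endpoint. The objectives tables name general safety and tolerability, measured by subject incidence of treatment-emergent events. The first-dose GI aim appears only in the dose justification. That is correct, so this is not a mismatch with the primary objective.

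Second, whether to titrate also depends on how the whole regimen is tolerated, and the comparison of cohort 9 with cohorts 12 and 13 is planned. That stands too. A reader might infer that Part C cannot inform the choice to titrate; the documents do not support going that far.

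Third, Part C has at most 12 open-label subjects. The dose level review looks at events and product administration through at least day 36, which covers every starting dose and the first step, though not days 43 and 57. This is a safety review during the study and does not commit the sponsor to a reported display.

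Fourth, the exploratory sections are redacted. A GI display could be hidden there, but SAP 9.6.2 is readable and speaks of all adverse event tables, so this is unlikely.

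A reader might also infer from the cohort 9 exits that withdrawals of consent over GI events will be missed in the table of events leading to withdrawal of product. The documents do not show this. Adverse event is a listed reason for stopping product (Protocol 7.1), the action taken is recorded for each event (11.4), reasons for leaving are summarised (SAP 9.2), and section 4.3 already ties those exits to GI events.

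**Conclusion.** The point holds as a gap between the aim that Protocol 4.3 gives Part C and the adverse event tables in SAP 9.6.2. No readable table shows whether GI events in cohorts 12 and 13 come at the starting dose or on escalation. In a cohort of 6, a cumulative 5/6 leaves the count after the step anywhere from 0 to 5.

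The consequence is limited to description. No hypothesis is tested, no error rate changes, and with at most 6 subjects per cohort any result by dose will be imprecise.

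The conclusion assumes that subject incidence over the treatment-emergent window means one count per subject, which the SAP implies without saying, and that no such table sits in redacted text. That the day 15 or day 29 step is the first 420 mg dose is inferred; the core point needs only that dose rises within subjects, which section 4.3 states. It is a cheap improvement worth making.

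**What to change.** In SAP 9.6.2, for cohorts 7 to 10, 12 and 13, add one descriptive table of the nausea/vomiting event of interest by dose number and dose level. For Part C a subject-level display would serve as well.

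- Count onsets within a fixed post-dose window, the same for every dose and cohort, for example 7 days.
- Use two denominators: subjects who received that dose, and all who started the cohort.
- Give exact intervals and label the comparison descriptive.
- State that weekly starting doses accumulate, so events reflect the regimen to date and not that dose alone.
- Keep the cumulative tables as planned.

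The cost is one derivation and one small table. Event onset dates (Protocol 11.4) and dosing dates (6.1.1) are already recorded, and no subjects, visits or procedures are added. The downside is that events starting after the window appear only in the cumulative table.

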2.2.2.4 Clinical Experience

As of **data entered by December** 2021, in the ongoing first in human (FIH) SAD trial of AMG 133 in subjects with obesity, **57** subjects have received a single dose of AMG 133 or placebo (cohorts **1 to 6 and cohort 11**). The blinded safety data through day 15 of the **840** mg SC dose cohort supports the dose range to be evaluated in this study. Single ascending doses of AMG 133 have been safe and generally well tolerated.

No significant adverse events or deaths have been reported, and most adverse events reported were mild consisting of nausea, vomiting, and dyspepsia. One subject in cohort 3 (140 mg dose) reported moderate adverse events associated with nausea, **abdominal discomfort**, and dyspepsia.

A total of 39 subjects have been enrolled in the MAD trial and have received 1 to 3 doses of AMG 133 or placebo. Most adverse events reported have been after the first dose of AMG 133 and were reported as mild consisting of headache, nausea, vomiting, and diarrhea. There have been no serious adverse events or deaths reported after single or multiple doses. Twenty-six percent of subjects did not receive the second or third dose of AMG 133 either due to adverse events or lost to follow up.

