7.2.2 Reasons for Removal From Study

Reasons for removal of a subject from the study are:

- Decision by sponsor
- Withdrawal of consent from study
- Death
- Lost to follow-up

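### The AE tables count events leading to withdrawal of product but not events leading to study exit, so AE-driven consent withdrawals in the MAD cohorts may go uncounted

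*SAP*

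**What the plan says.** **AE tables.** SAP 9.6.2 has subject incidence "summarized for all TEAEs, SAEs, TEAEs leading to withdrawal of IP, fatal AEs" and events of interest. SAP Table 9-1 words the withdrawal row more broadly, as "AEs leading to withdrawal from IP or other protocol-required therapies". Neither names events leading to study discontinuation, and SAP Section 5 does not define when an AE counts as leading to withdrawal.

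**Disposition.** SAP 9.2 separately summarises subjects who "discontinued IP and reason for discontinuing, completed study, discontinued study and reason for discontinuing".

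**Reasons available to sites.** Protocol 7.2.2 gives four reasons for leaving the study: sponsor decision, "Withdrawal of consent from study", death and loss to follow-up. Protocol 7.1, on stopping product or procedures, lists both adverse event and subject request, with no rule for choosing when an AE prompts the request. Protocol 7.2 defines consent withdrawal to include no longer wanting study therapy, so that one code can absorb an AE-driven stop.

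**What has happened.** Protocol 4.3 reports that "50% of subjects in cohort 9 withdrew consent after receiving the 420 mg dose on day 1 due to GI-related adverse events". It also says "Approximately 26% of subjects in the MAD trial discontinued the study prior to" the second dose. Protocol 2.2.2.4 says "A total of 39 subjects have been enrolled in the MAD trial" and that 26% "did not receive the second or third dose of AMG 133 either due to adverse events or lost to follow up"; consent withdrawal is not mentioned there.

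**The concern.** Exits caused by AEs bear directly on tolerability, which is part of the primary objective, and the other planned AE summaries separate the regimens poorly. Protocol 4.3 puts mild GI events after the first dose at about 90% of MAD subjects, so overall GI incidence is near its ceiling. The SAP 9.6.2 tables carry no severity breakdown, and SAP Section 10 drops tabulation by relationship to study drug. AE-driven exit is one of the few measures left that could distinguish a tolerable first dose from one that is not.

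First-dose GI tolerability is also the stated reason for the titrated Part C cohorts (Protocol 4.3). A reader of the study report will set Part B beside Part C, even though no formal comparison is planned. If an AE-driven exit is coded as an AE at one site and as consent at another, that reading depends on coding practice. Dosing intervals may add to this. Part B doses are 28 days apart, so a GI event can resolve before the next dose is due. Part C begins with weekly doses, so an event is more likely to be ongoing at a dosing visit and to be coded as stopping product. This last step is inference, not something the documents state.

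**Working it through.** **1. The plan's own figure.** Inputs: 39 MAD subjects and 26% (Protocol 2.2.2.4). 0.26 × 39 = 10.1. Check: 10/39 = 25.6%, which rounds to 26%; 9/39 = 23.1% and 11/39 = 28.2% do not. So about 10 subjects, active and placebo together, and including losses to follow-up. The two protocol sections differ on timing: 4.3 says before the second dose, 2.2.2.4 says second or third.

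**2. Cohort 9.** Inputs: 50% (Protocol 4.3); planned allocation 6 active and 2 placebo (Protocol Table 7). The denominator is not stated, so both readings are shown.

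- Active subjects only: 0.50 × 6 = 3, giving 3/6 = 50% on AMG 133.
- All 8 planned subjects: 0.50 × 8 = 4. With 0 to 2 of the four on placebo, the active count is 4 − 2 = 2 up to 4 − 0 = 4, giving 2/6 = 33% to 4/6 = 67%.

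If these 3 or 4 subjects are among the 10 MAD dropouts (an assumption), they are 3/10 = 30% to 4/10 = 40% of them.

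**3. Following one such subject through the plan.** The subject has nausea after dose 1 and withdraws consent before day 29.

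| Record | What can be entered | Where it is reported |
|---|---|---|
| Reason for leaving study (Protocol 7.2.2) | Consent withdrawal; no AE option | SAP 9.2, no AE term |
| Reason for stopping product (Protocol 7.1) | Adverse event or subject request; no rule | SAP 9.2 |
| Action taken for the AE (Protocol 11.4) | Product discontinued, or not | Not stated; the likely source for SAP 9.6.2 and Table 9-1 |

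Only the first row is fixed by the documents. The other two depend on the site. The AE-withdrawal table can therefore include all of these subjects or none.

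**4. Part A.** There is one dose, on day 1, so no product remains to be withdrawn and the SAP 9.6.2 row has essentially nothing to count. The Table 9-1 wording leaves one route open: Protocol 6.1.4 places the test done in cohorts 1 to 5 and 11 under other protocol-required therapies, and it is repeated on day 7. An AE that stopped that test could be counted. An AE that led a subject to leave the study during follow-up to day 150 would not be.

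**The case against.** The strongest reply is that the information is not lost. SAP 9.2 reports reasons for stopping product, where adverse event is an available reason, alongside reasons for leaving the study. Protocol 11.4 requires an action taken for every AE, so a consent withdrawal does not prevent the AE from being marked as stopping product. SAP 9.6.8 summarises the number of doses received. Half a cohort leaving at 420 mg would be visible in disposition and exposure however the reasons were coded. First-dose nausea and vomiting are reported as TEAEs and as events of interest. The study is descriptive and tests no hypothesis.

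All of this stands, and it limits the point. A reader might infer that the AE-withdrawal table is the only place where tolerability exits are reported; SAP 9.2 shows otherwise. A reader might infer that MAD dropouts in general were recorded as consent withdrawals. The documents say this for cohort 9 only, in a narrative sentence, and Protocol 2.2.2.4 attributes missed doses to AEs or loss to follow-up, which can be read as a product-level account consistent with 4.3. A reader might also infer that the Part A row is empty by construction; the Table 9-1 wording does not quite allow that.

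The reply does not close the gap. Disposition would show that subjects left, but under 7.2.2 the study-level reason cannot be an AE, and no AE term is attached. Nothing tells sites which product-level reason to use, and nothing tells the programmer which field defines an AE leading to withdrawal.

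**Conclusion.** The gap is real and should be fixed; it is not critical. As written, the AE-withdrawal table could show anywhere from none to all of the AE-driven MAD exits. In cohort 9 that means 3 of 6 AMG 133 subjects if the 50% refers to active subjects, or 2 to 4 of 6 if it refers to 8 planned subjects. In Part A no AE table would count an AE-driven study withdrawal.

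The cohort 9 figures assume the planned 6:2 split was enrolled. The figure of about 10 MAD dropouts is not a count of AE-driven exits, since it includes losses to follow-up and pools active with placebo. A reader might go further and conclude that the report will show no AE withdrawals at 420 mg. The documents do not support that: no CRF data are shown, and both the product-level reason and the action-taken field could capture these subjects.

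**What to change.** 1. **SAP Table 9-1 and 9.6.2.** Add a row for TEAEs leading to discontinuation from study, by dose phase and actual treatment group. Include consent withdrawal or subject request that the site attributes to an AE. State the CRF field or fields that define an AE leading to withdrawal of product and of study, and use one wording in both places.
2. **Recording.** Add adverse event to the study-discontinuation reasons in Protocol 7.2.2, or keep the list and link the AE to the withdrawal on the CRF. Either way, give sites a rule for choosing between adverse event and subject request in 7.1. This concerns coding only and does not alter when anyone stops.
3. **Existing data.** Reconcile Protocol 2.2.2.4 with 4.3 on the reasons for and timing of the 26%, and state the denominator of the cohort 9 figure. Before lock, query sites on the roughly 10 MAD discontinuations and accept only attributions already documented at source.

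The cost is SAP wording, a CRF instruction or link, and a few queries. The drawback is that some attribution will be retrospective, so the report should flag which entries were made after the query.
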